(±1 hour) for a total of three doses. Patients randomized to Group 2 will receive 1.0 mg/kg of Auxora intravenously every 24 hours (±1 hour) for a total of three doses. Patients randomized to Group 3 will receive 0.5 mg/kg of Auxora intravenously every 24 hours (±1 hour) for a total of three doses. Patients randomized to Group 4 will receive emulsion without any active pharmaceutical ingredient. Patients in Group 4 will receive one of three randomly assigned dose volumes, 1.25 mL/kg, 0.625 mL/kg, or 0.3125 mL/kg, which will be administered intravenously every 24 hours (±1 hour) for a total of three doses. (Section 5.3) The dosing will be based on actual body weight obtained at the time of hospitalization or screening for the study. As described in the pharmacy manual, the upper limit of the volume of Auxora and volume of Placebo that will be administered will be 156.25 mL. The sponsor, investigators, pharmacists, and patients will be blinded to the assigned group. In the event of a medical emergency, investigators will be able to receive the treatment assignment if required to provide optimal care of the patient.

For all 4 groups, a study physician or appropriately trained delegate will perform study-specific assessments at screening, at the baseline assessment, immediately prior to the SFISD, and then every 24 hours until 240 hours after the SFISD, or until discharge if earlier. If patients remain hospitalized at Day 12, assessments will then be performed every 48 hours starting on Day 12 until Day 28, or until discharge if earlier. Patients discharged from the hospital before Day 25 will return at Day 30 (+5 days) to perform the Day 30 assessments. If patients are discharged on Days 25-29, the Day 30 assessments may be performed prior to discharge.

Patients will receive another CECT of the abdomen/pancreas at the Day 30 (± 5 days) visit. All CECTs performed as SOC after randomization and before the Day 30 CECT will also be captured. A blinded central reader will read the Screening, Day 30, and any SOC CECTs obtained between randomization and the Day 30 visit.

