- Determine if the patient met the medically indicated discharge criteria in the previous 24 hours (see Section 5.3)
- Perform AE/SAE assessment
- Prior to the infusion of the third dose of study drug:
 - Draw blood samples for CBC, differential, platelets, Serum Procalcitonin and Serum Chemistries – analyze at local lab. Testing may be performed on blood drawn in the previous 12 hours.
 - O Draw blood sample for Serum IL-6 send to central lab. Testing may be performed on blood drawn in the previous 12 hours.
 - Obtain urine sample for Urine NGAL send to central lab. Testing may be performed on urine collected in the previous 12 hours.
- Start the infusion of third dose of study drug 48 hours (±1 hours) from the SFISD (see Section 5.3)
 - o Record the time that the infusion starts and finishes
- Assess whether patient discharge is upcoming and whether mGCSI-DD worksheets need to be dispensed per Section 8.12.10.

8.7 72 hours

For patients who remain hospitalized 72 hours from the SFISD:

- Record concomitant medications
- Record weight closest to the scheduled time of assessment
- Record vital signs closest to the scheduled time of assessment
- Record the patient's pain using the PNRS closest to the scheduled time of assessment
- Record SpO₂ and the FiO₂ (see Section 8.12.6) closest to the scheduled time of assessment
- Determine if, and when the patient tolerated solid food in the previous 24 hours (see Section 5.2)
- Determine if the patient met the medically indicated discharge criteria in the previous 24 hours (see Section 5.3)
- Perform AE/SAE assessment
- Draw blood samples for CBC, differential, platelets, Serum Procalcitonin and Serum Chemistries analyze at local lab. Testing may be performed on blood drawn in the previous 12 hours or + 2 hours from assessment.
- Draw blood sample for Serum IL-6 send to central lab. Testing may be performed on blood drawn in the previous 12 hours or + 2 hours from assessment.
- Draw blood sample for PK \pm 2 hours send to central lab

- Obtain urine sample for Urine NGAL send to central lab. Testing may be performed on urine collected in the previous 12 hours or + 2 hours from assessment.
- Assess whether patient discharge is upcoming and whether mGCSI-DD worksheets need to be dispensed per Section 8.12.10.

8.8 96, 120, 144, 168, 192, 216, 240 hours (±4 hours)

For patients who remain hospitalized 96, 120, 144, 168, 192, 216, and 240 hours from the SFISD:

- Record concomitant medications

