8.11 Discharge Date

The time and date of discharge will be recorded as well as if the patient meets criteria for medically indicated discharge. All patients will be trained to complete the mGCSI-DD and will complete the mGCSI-DD before leaving the hospital. If patients are discharged on Days 25-29, they may complete the Day 30 assessments on the day of discharge. Following discharge, the Investigator or designee should contact patient by telephone once per week to confirm diary completion and patient agrees to return for Day 30 visit.

If a patient is admitted to a hospital following discharge but prior to Day 30 visit, Investigator will report the reason for the hospitalization as per serious adverse event reporting guidelines (See Section 9.2 and Section 9.7). As the patient is still within the study period, investigators or designee should resume collection of study procedures as per Schedule of Events (See Appendix 8). If patient is not admitted to the hospital where the study is being conducted, investigators are asked to record any procedures (i.e., invasive mechanical ventilation) received while patient was admitted during the study period within an unscheduled procedures form in the eCRF.

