8.12.10 Modified ANMS GCSI-Daily Diary (mGCSI-DD)

The ANMS GCSI Daily Diary was designed to assess gastrointestinal symptoms associated with idiopathic and diabetic gastroparesis. It has been shown to be a reliable tool to evaluate dysmotility in patients with AP (Ma 2016). It will be used to assess gastrointestinal symptoms associated with AP in an exploratory manner. The mGCSI-DD has a 24-hour recall; thus, all items are designed to be self-administered on a daily basis.

The patient training for completing the daily diary is provided by the PI or appropriately trained delegate. Patients should understand their disorder: AP, where there is an abnormally delayed emptying of food from the stomach because of inflammation in the pancreas. The mGCSI-DD recording sheet and instructions are reviewed with the patient prior to the patient starting the recording of daily symptoms in the diary. The symptom severity response items are reviewed: "For each symptom listed below, please mark with an X the box that best describes the worst severity of each symptom during the past 24 hours. The next question asks you to record the number of times vomiting occurred in the last 24 hours. Please record the number of vomits (throwing up with food or liquid coming out) that occurred in the last 24 hours. Record zero, if you have not vomited during the past 24 hours. If you vomited, write down the number of all vomits. If you vomited once, record one. If you vomited three times during the day, record three. If you vomited three times, whether it was during the same trip to the bathroom or three separate trips, record three as the number of episodes of vomiting."

Patients discharged before Day 25 will complete the daily diary on the day of discharge, and then after discharge, daily at bedtime until the Day 30 visit.

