8.7.2 Time to Medically Indicated Discharge

The time to medically indicated discharge is the number of days from the SFISD to the first date of meeting the criteria defining medically indicated discharge:

- the patient tolerates solid food, as defined by the main analytical approach; and
- abdominal pain is controlled or resolved, which will be defined by a reduction in pain, as assessed by the PNRS scale, of ≥50% from the peak level in the first 24 hours and no use of opioids; and
- there is no clinical evidence of an infection requiring continued hospitalization.

In patients who do not meet the criteria for medically indicated discharge when discharged from the hospital, the time to medically indicated discharge will be defined as 8am on the first of three consecutive days where the 4 criteria are met for the mGCSI-DD as defined in 8.6.3. If a patient is discharged not meeting the criteria for medically indicated discharged and does not meet criteria for the mGCSI-DD or has not completed the mGCSI-DD, the time to medically indicated discharge will be censored at 168 hours. If the patient dies while hospitalized, the time to medically indicated discharge will be censored at Day 30.

The time to medically indicated discharge will be summarized using Kaplan-Meier analyses. The medians and quartiles of time-to-events will be summarized for each study group. The time to medically indicated discharge will be compared between each Auxora treatment group and placebo group using stratified log-rank test stratified by sex (male or female) and the risk for organ failure (higher or lower). Prohibited immunosuppressive medications or immunotherapies and treatment discontinuation will be ignored (treatment policy strategy).

Protocol CM4620-203 CONFIDENTIAL Page 19 of 31

The proportion and 95% CI of patients who meet the medical discharge criteria by the 96-hour visit and the date of discharge will be displayed using a Clopper-Pearson interval and will be compared between each Auxora treatment group and placebo group using a Cochran-Mantel-Haenszel test stratified by the eCRF recorded sex (male or female) and the risk for organ failure (higher or lower) based on eCRF data. Prohibited immunosuppressive medications or immunotherapies and treatment discontinuation will be ignored (treatment policy strategy).

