The correlation between meeting the medically indicated discharge criteria on the day of discharge with each of the following events, hospital readmission for acute pancreatitis, the development of pancreatic necrosis/necrotizing pancreatitis, and worsening CTSI score at Day 30 from Screening, will be summarized by treatment groups by Matthews correlation coefficient (MCC).

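### SAP 8.7.2 judges pain control at discharge by a PNRS score, but the protocol schedules no PNRS at discharge and none between 240 hours and Day 30

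*Protocol*

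**What the plan says.** **What the SAP needs.** SAP 8.7.2 lists three criteria for medically indicated discharge: solid food tolerated, pain controlled or resolved, and no infection that requires a longer stay. The pain criterion is numerical, "which will be defined by a reduction in pain, as assessed by the PNRS scale, of ≥50% from the peak level". The reference peak is the one reached during the initial 24-hour period, and opioid use must be absent. Three analyses use the resulting status:

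- time to medically indicated discharge (Kaplan-Meier, stratified log-rank);
- the proportion meeting the criteria by the 96-hour visit and by the date of discharge (CMH);
- Matthews correlations of "meeting the medically indicated discharge criteria on the day of discharge" with readmission for acute pancreatitis, with pancreatic necrosis, and with a worse CTSI score.

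**What the protocol collects.** Assessments run "every 24 hours until 240 hours after the SFISD, or until discharge if earlier" (Protocol 3.1). At each of these visits (8.5 to 8.8) staff are to "Record the patient's pain using the PNRS closest to the scheduled time of assessment". The 72-hour list applies "For patients who remain hospitalized 72 hours from the SFISD", and the later lists are conditional in the same way. The Days 12 to 28 list (8.9) has no PNRS. SAP 8.7.10 agrees: scores run to Day 10 and then at Day 30.

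**What is done at discharge.** Protocol 8.11 asks for two things: "The time and date of discharge will be recorded as well as if the patient meets criteria for medically indicated discharge", and the diary ("All patients will be trained to complete the mGCSI-DD and will complete the mGCSI-DD before leaving the hospital"). Neither 8.11 nor Appendix 8 lists a PNRS at discharge. Under 8.10, patients discharged on Days 25-29 may have the Day 30 assessments, which include the PNRS, on that day.

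**The concern.** The SAP replaces a clinical judgement of pain with a threshold that only a PNRS value can show, and applies it at a moment when none is scheduled. Patients leave when they have improved, so some of the fall in pain may come after the last scheduled score. For them the data cannot show that the criterion was met.

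The endpoint is secondary, but the second primary objective (Protocol 2.1, SAP 2.1) is stated in terms of it: time to medically indicated discharge in early food-tolerance responders against non-responders. A status that depends on where discharge falls relative to the visit clock adds error to that comparison, to the discharge proportion and to the correlations.

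The protocol already handles the same timing problem for another measurement. If a patient leaves after the third infusion and before 72 hours, the PK sample is taken before discharge (8.12.8). Nothing similar is written for the PNRS.

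**Working it through.** The plan gives no figure on this point to reproduce. The check sets the criterion against the collection schedule and computes how old the last score can be.

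**Step 1. Each part of the criterion against its recording.**

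| Part of the SAP 8.7.2 criterion | When it is recorded | Known at discharge? |
|---|---|---|
| Solid food tolerated | Time of the tolerated meal (Protocol 5.2) | Yes |
| No opioid use | Time of each dose given (8.12.2) | Yes |
| No infection requiring a longer stay | Discharge criteria checked at each visit (8.5-8.9) and at discharge (8.11) | Yes |
| PNRS at least halved | Baseline, 24-hourly to 240 h, Day 30 (8.2, 8.5-8.8, 8.10, Appendix 8) | Only if a scheduled score falls shortly before leaving |

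The PNRS is the only part read solely at fixed visits.

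**Step 2. Age of the last score, up to 240 h.** Longest gap = nominal interval + window of the earlier visit + window of the later visit. Appendix 8 gives windows of ±1 h at 24 and 48 h, ±2 h at 72 h and ±4 h from 96 h on.

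| Interval | Nominal | Longest with windows |
|---|---|---|
| 24 to 48 h | 24 h | 24 + 1 + 1 = 26 h |
| 48 to 72 h | 24 h | 24 + 1 + 2 = 27 h |
| 72 to 96 h | 24 h | 24 + 2 + 4 = 30 h |
| Each later interval to 240 h | 24 h | 24 + 4 + 4 = 32 h |

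Patients are asked to stay for all three doses (Protocol 5.3), so the rows from 48 h on matter most.

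**Step 3. Age of the last score, after 240 h.** Protocol 8.9 counts days from SFISD. A Day 12 discharge gives 12 × 24 − 240 = 48 h, or 2 days. A Day 24 discharge gives 24 × 24 − 240 = 336 h, or 14 days. If days are counted as in SAP 8.1.4.2, with the SFISD date as Day 1, Day 24 gives 23 × 24 − 240 = 312 h, or 13 days. From Day 25 the Day 30 score may be taken on the day of discharge.

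**Step 4. What happens to an affected patient.** Let P be the first-24-hour peak. Suppose the last scheduled score is above P/2, pain then falls to P/2 or less without opioids, and the patient leaves before the next visit.

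- *Proportion by the date of discharge, and the correlations.* No PNRS at or below P/2 exists. Read literally, the criterion is not met.
- *Time to event.* SAP 8.7.2 moves the patient to the diary rule of 8.6.3: 8am on the first of three consecutive days that satisfy four diary items. If the diary is missing or does not qualify, the time is censored at 168 h.
- *Link between the two.* SAP 8.7.2 does not say whether a diary-derived date on the day of discharge counts as met in the proportion or the correlations.

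**Step 5. Is there a rule for a missing end value?** The SAP states LOCF for CTSI (8.7.5), necrosis (8.7.6) and SIRS (8.7.7). It states none for the PNRS in 8.7.2, and does not name the score that decides at discharge. Carrying the last score forward would give the same answer as the literal reading.

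**The case against.** **The SAP does not say that these patients are scored as failures.** A reader might infer that it does. It gives no rule for a discharge without a concurrent score, so the literal reading is only the most natural one.

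**The diary fills much of the gap.** "Patients discharged before Day 25 will complete the daily diary on the day of discharge" (Protocol 8.12.10), it has an abdominal pain item, and the rule in SAP 8.6.3 covers days at or after discharge. A patient who leaves well and stays well can get an event time on or near the day of discharge, and the endpoint is counted in days. This stands for the time-to-event analysis, with a limit: each item asks for the worst severity in the past 24 hours, so pain earlier on the day of discharge can fail that day. It does not settle the proportion or the correlations.

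**The investigator's record at discharge could serve.** SAP 8.7.2 does not refer to it, and it applies a different test. Protocol 5.3 accepts pain controlled with medications, while the SAP requires no opioids. Those passages need reconciling in any case. A patient still on opioids fails the SAP criterion whatever the PNRS shows, so a discharge score changes nothing for that patient.

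**Some discharges do have a usable score.** The analyses go by date, so a visit earlier on the same day counts. A discharge at 70 h lies at the edge of the 72 (±2) h window, and the score could be taken before leaving. Both points stand and narrow the gap.

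**A frequency is tempting, but the documents do not support one.** Suppose pain is the last criterion met, at a time unrelated to the visit clock, and discharge follows D hours later. The chance that no score falls between is 1 − D/24: 83%, 75%, 50% and 25% for D = 4, 6, 12 and 18 h. If the early 4 h window (visits from 96 h on) is always used, it is 1 − (D + 4)/24: 67%, 58%, 33% and 8%. The documents give no D and do not show that pain is the last criterion met. Same-date visits lower the figures further.

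**Conclusion.** The mismatch holds. The pain criterion rests on a score that is not scheduled when the status is determined. Up to 240 h the last score may be about 24 h old, or 27 to 32 h with windows from the 48-hour visit on. After 240 h it may be about 14 days old for a Day 24 discharge. Slow recoverers are therefore exposed as well as early leavers, apart from Days 25-29 discharges who have the Day 30 score that day.

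The consequence is limited. The discharge proportion and the three Matthews correlations can take a wrong negative, on a literal reading of a SAP that states no rule. In the time-to-event analysis the usual result is a diary-based time, with censoring at 168 h only if the diary is missing or does not qualify.

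A reader might infer that an effective arm, with faster pain relief and earlier discharge, loses the most events. The documents do not show this. Faster relief could equally mean that the score has already halved by 24 or 48 h, and a patient moved to the diary rule has not necessarily lost an event. The direction of any bias between arms is not established, nor is the number of patients affected.

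This is a cheap improvement to a secondary endpoint named in a primary objective. The primary endpoint analysis does not use the PNRS threshold.

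**What to change.** 1. In Protocol 8.11 and Appendix 8, add a PNRS on the day of discharge before the patient leaves, with the record of any opioid given in the previous 2 hours (8.12.11).
2. Add the PNRS to the Days 12-28 visits (8.9, Appendix 8). A discharge score alone would not show when pain came under control during a long stay.
3. In SAP 8.7.2, state that the discharge-day PNRS decides the pain criterion on the day of discharge. State also whether a diary-derived date counts as met in the discharge proportion and the correlations.

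Cost: one 0-10 rating per patient at discharge, a few more for long stays, an eCRF field and short SAP text. No extra visit or procedure is needed.

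If collection can no longer change, the SAP should still say, before unblinding, which score or record decides the criterion when no PNRS was taken at discharge.

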8.9 Days 12 to 28 (± 4 hours)

For patients who remain hospitalized 12, 14, 16, 18, 20, 22, 24, 26, and 28 days from the SFISD:

• Determine if, and when the patient tolerated solid food in the previous 48 hours

CM4620-203

- Determine if the patient met the medically indicated discharge criteria in the previous 48 hours (see Section 5.3)
- Perform AE/SAE assessment
- Assess whether patient discharge is upcoming and whether mGCSI-DD worksheets need to be dispensed per Section 8.12.10.
- If the patient remains hospitalized at Day 14 and Day 21, request the patient record their symptoms at bedtime using the mGCSI-DD worksheet (see Section 8.12.10).

8.10 Day 30 (±5 days)

Patients who had been discharged from the hospital before Day 25, should return on Day 30 for the following assessments:

- Record the investigator's opinion of etiology of the AP episode
- Record weight
- Perform CECT of the pancreas. May be performed in the 5 days before or after the visit.
- Collect mGCSI-DD worksheets from the patient
- Record concomitant medications
- Record vital signs
- Record the patient's pain using the PNRS
- Record SpO₂ and the FiO₂ (see Section 8.12.6)
- Perform AE/SAE assessment
- Draw blood samples for CBC, differential, platelets, Serum Procalcitonin, and Serum Chemistries - analyze at local lab
- Draw blood sample for Serum IL-6 send to central lab
- Draw a blood sample for PK send to central lab
- Obtain sample for Urine NGAL send to central lab

For patients discharged from the hospital on Days 25-29, the Day 30 assessments may be performed on the Day of discharge.

Patients who are discharged from the hospital on Days 25-29 will not complete the mGCSI-DD after discharge. They will only complete it on the day of discharge.

For patients who remain hospitalized on Day 30, the following additional assessment will be performed:

- Determine if, and when the patient tolerated solid food in the previous 48 hours
- Determine if the patient met the medically indicated discharge criteria in the previous 48 hours (see Section 5.3)

For patients that do not return for Day 30 visit and have not withdrawn consent, the Investigator or designee will continue to contact patient by phone to return for on-site visit up to eight weeks following visit date. Although an out of window visit assessment would be considered a protocol deviation, investigators should attempt to obtain as much as possible all of the Day 30 visit assessments, including the Day 30 CECT.

If patient is not reachable by phone after four weeks following the planned Day 30 visit, the Investigator or designee will send certified letter to last known address to request patient to contact Investigator to either schedule Day 30 visit or at least confirm patient is still alive by telephone. If patient does not respond to certified letter or if patient had withdrawn consent, the Investigator or designee will check public records (e.g., vital records search) to determine if the patient had died prior to the scheduled Day 30 visit or can be assumed alive for the purposes of study follow-up.

8.11 Discharge Date

The time and date of discharge will be recorded as well as if the patient meets criteria for medically indicated discharge. All patients will be trained to complete the mGCSI-DD and will complete the mGCSI-DD before leaving the hospital. If patients are discharged on Days 25-29, they may complete the Day 30 assessments on the day of discharge. Following discharge, the Investigator or designee should contact patient by telephone once per week to confirm diary completion and patient agrees to return for Day 30 visit.

If a patient is admitted to a hospital following discharge but prior to Day 30 visit, Investigator will report the reason for the hospitalization as per serious adverse event reporting guidelines (See Section 9.2 and Section 9.7). As the patient is still within the study period, investigators or designee should resume collection of study procedures as per Schedule of Events (See Appendix 8). If patient is not admitted to the hospital where the study is being conducted, investigators are asked to record any procedures (i.e., invasive mechanical ventilation) received while patient was admitted during the study period within an unscheduled procedures form in the eCRF.

